7.3.5. Blood Pressure and Heart Rate

Blood pressure will be measured in the subject's dominant arm and recorded to the nearest mmHg. The same arm will be used throughout the study. All blood pressure in this study will be measured with the subject in the sitting position after resting for at least 5 minutes. The same blood pressure cuff, which has been properly calibrated, should be used to measure blood pressure each time. When the timing of these measurements coincides with a blood collection, blood pressure and heart rate should be obtained first.

7.3.6. Electrocardiogram

Single twelve (12) lead ECGs will be obtained on all subjects. All scheduled ECGs should be performed after the subject has rested quietly for at least 10 minutes. ECGs are to be transferred from the sites to a central vendor for assessment. The ECG results provided by the central vendor will be stored in the study database and used for the planned analysis.

If QTc exceeds 450 msec, or QRS exceeds 120 msec, the ECG should be repeated two more times and the average of the three QTc or QRS values should be used to determine the subject's eligibility.

7.3.7. QuantiFERON Test

A QuantiFERON Gold®™ test will be used to test for active / latent tuberculosis (TB). A description of the QuantiFERON Gold test follows:

“This Enzyme-linked Immunosorbent Assay (ELISA) test detects the release of Interferon-gamma (IFN- γ) in fresh heparinized whole blood from sensitized persons when it is incubated with mixtures of synthetic peptides simulating two proteins present in *M. tuberculosis*: Early Secretory Antigenic Target--6 (ESAT-6) and Culture Filtrate Protein-10 (CFP-10). ESAT-6 and CFP-10 are secreted by all *M. tuberculosis* and pathogenic *M. bovis* strains. Because these proteins are absent from all Bacille Calmette-Guérin (BCG) vaccine strains and from commonly encountered NonTuberculous Mycobacteria (NTM) except *M. kansasii*, *M. szulgai*, and *M. marinum*, QFT-G is expected to be more specific for *M. tuberculosis* than tests that use tuberculin Purified Protein Derivative (PPD) as the antigen.”

Subjects with a documented positive IGRA TB test (eg, QuantiFERON®-TB GOLD (QFT-G) performed within 12 weeks prior to Screening are excluded. The specific IGRA method, or test, used should comply with local country-specific guidelines. A subject who is currently being treated for either latent or active TB infection is to be excluded. The type (name) and results of the IGRA TB test must be known and located in source documentation.

7.3.8. Chest X-Ray

Chest radiograph (posterior-anterior and lateral views are recommended, however local guidelines should be followed) is required at Screening. A chest X-ray or other appropriate diagnostic chest imaging modality [ie, Computerised Tomography (CT) or Magnetic Resonance Imaging (MRI)] performed within 12 weeks prior to screening and read by a qualified radiologist with no evidence of current, active TB or previous inactive TB, general infections, heart failure or malignancy may substitute for the Chest X-ray taken at Screening. Documentation of the official reading must be located and available in the source documentation.

CCI [REDACTED]

[REDACTED]

[REDACTED]

[REDACTED]

[REDACTED]

090177e190fc2bd0Approved\Approved On: 27-May-2019 05:59 (GMT)

CCI [Redacted]

[Redacted]

[Redacted]

[Redacted]

[Redacted]

[Redacted]

CCI [Redacted]

CCI

090177e190fc2bd0\Approved\Approved On: 27-May-2019 05:59 (GMT)

7.6. PF-06650833 Triggered Requirements

7.6.1. Hypotension, and Tachycardia

Symptomatic hypotension should be treated with supportive measures (eg, supine or Trendelenburg positioning) and fluid resuscitation as deemed appropriate by the Investigator. Tachycardia associated with hypotension would likely respond to the measures to treat the hypotension, so no specific targeted treatment may be needed. Isolated tachycardia should be treated expectantly and with supportive measures as for hypotension. Specific pharmacologic interventions to treat hypotension or tachycardia should be avoided if possible.

7.6.2. Potential Cases of Acute Kidney Injury

Abnormal values in serum creatinine (SCr) concurrent with absence of increase in BUN (blood urea nitrogen) that meet the criteria below, in the absence of other causes of kidney injury, are considered potential cases of acute kidney injury and should be considered important medical events. An increase of ≥ 0.3 mg/dL (or ≥ 26.5 $\mu\text{mol/L}$) in serum creatinine relative to subjects' own baseline measurement should trigger another assessment of SCr as soon as practically feasible, preferably within 48-hours from awareness.

If the second assessment (after the 1st observations of ≥ 0.3 mg/dL (or ≥ 26.5 $\mu\text{mol/L}$) in serum creatinine relative to subjects' own baseline measurement) is ≥ 0.4 mg/dL (or ≥ 35.4 $\mu\text{mol/L}$), the subject should be discontinued from the study and adequate, immediate, supportive measures taken to correct apparent acute kidney injury.

Subjects should return to the investigational site and be evaluated as soon as possible, preferably within 48-hours from awareness of the second assessment confirming abnormal SCr result. This evaluation should include laboratory tests, detailed history, and physical assessment. In addition to repeating SCr, laboratory tests should include: serum blood-urea-nitrogen, serum creatine kinase, serum electrolytes (including at a minimum potassium, sodium, phosphate/phosphorus, calcium), in addition to urinary dipstick, urine microscopic examination, and urinary indices. All cases confirmed on repeat testing as meeting the laboratory criteria for acute-kidney-injury, with no other cause(s) of laboratory abnormalities identified should be considered as potential cases of drug-induced kidney injury irrespective of availability of all the results of the investigations performed to determine etiology of the abnormal SCr. Evaluation by a trained nephrologist may be appropriate if kidney injury is suspected.

If ≥ 2 subjects in a given period are noted to have 2 *consecutive* SCr results of ≥ 0.3 mg/dL (or ≥ 26.5 $\mu\text{mol/L}$), an assessment of whether the finding may be considered adverse drug reaction should be undertaken.

CCI [REDACTED]

[REDACTED]

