6.3. Subject Withdrawal/ Discontinuation Criteria

A subject may withdraw from the study at any time at their own request, or they may be withdrawn at any time at the discretion of the investigator or Pfizer for safety or behavioral reasons, or the inability of the subject to comply with the protocol-required schedule of study visits or procedures at a given study site.

The sponsor's Clinical team should be consulted as soon as possible and subjects should be discontinued if any of the following occur during the study:

- Subjects who have a flare of RA requiring treatment with prohibited concomitant medication should be discontinued.

- Subjects who require rescue doses of acetaminophen/paracetamol or opioid for more than 10 consecutive days for treatment of increased RA symptoms should be discontinued.
- Subjects interrupting study medication for more than 7 consecutive days, or patients who are less than 80% compliant with the dosage regimen for any two consecutive visit periods should be withdrawn from the study.
- Subjects manifesting a serious infection, defined as any infection (viral, bacterial, and fungal) requiring hospitalization or parenteral antimicrobials.
- Any laboratory (defined by changes in serum creatinine or eGFR) or clinical manifestation of acute renal injury (Section 7.6.2 CCI [REDACTED]) [REDACTED]

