7.7. Triggered Requirements

Condition	Action
Neutrophil counts <1000 cells/mm ³	The subject should return to the study site for prompt retesting, ideally within 3-5 days .
Platelet counts <100,000 platelets/mm ³	The subject should return to the study site for prompt retesting, ideally within 3-5 days .
Lymphocyte counts <500 lymphocytes/mm ³	The subject should return to the study site for prompt retesting, ideally within 3-5 days .
Any single AST and/or ALT elevation >3 times the upper limit of normal (ULN)*	The subject should return to the study site for prompt retesting, ideally within 3-5 days .*
Any single hemoglobin value <8.0 g/dL or one that drops ≥2 g/dL below baseline.	The subject should return to the study site for prompt retesting, ideally within 3-5 days .
Any serum creatinine increase >50% over the average of screening (most recent value prior to baseline) and baseline values OR an absolute increase in serum creatinine >0.3 mg/dL (>26.5 μmol/L) over the average of screening (most recent value prior to baseline) and baseline values	The subject should return to the study site for prompt retesting, ideally within 3-5 days . If the second assessment (after the 1 st observations of ≥0.3 mg/dL (or ≥26.5 μmol/L) in serum creatinine relative to subjects' own baseline measurement) is ≥0.4 mg/dL (or ≥35.4 μmol/L), the subject should be discontinued from the study and adequate, immediate, supportive measures taken to correct apparent acute kidney injury.

* The subject must return to the study site for prompt retesting and include the following tests: albumin, creatine kinase (CK), total bilirubin, direct and indirect bilirubin, GGT, PT/INR, and alkaline phosphatase. Additional investigations include a detailed history, occupational exposure, sexual history, travel history, history of contact with a jaundiced subject, surgery, blood transfusion, history of liver or allergic disease, work exposure, history of ethanol, recreational drug and dietary supplement consumption. Testing for acute hepatitis A, B or C infection and biliary tract imaging may be considered. A subject with a total bilirubin value ≥2 × ULN concurrently may need to return to the investigational site and be evaluated as soon as possible, preferably within 48 hours from awareness of the abnormal results (refer to 8.4.2).

090177e190fc2bd0Approved\Approved On: 27-May-2019 05:59 (GMT)

Condition	Action

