2 sequential AST or ALT elevations ≥ 3 x ULN with a total bilirubin value ≥ 2 x ULN	Treatment with all study drugs will be discontinued and the subject withdrawn from this study.
2 sequential AST or ALT elevations ≥ 3 x ULN with an elevated INR	Treatment with all study drugs will be discontinued and the subject withdrawn from this study.
2 sequential AST or ALT elevations ≥ 3 x ULN accompanied by symptoms consistent with hepatic injury	Treatment with all study drugs will be discontinued and the subject withdrawn from this study.
2 sequential AST or ALT elevations ≥ 5 x ULN, regardless of Total Bilirubin or accompanying symptoms	Treatment with all study drugs will be discontinued and the subject withdrawn from this study.
Two sequential hemoglobin values < 8.0 g/dL or a decrease of more than 30% from baseline value;	Treatment with all study drugs will be discontinued and the subject withdrawn from this study. Follow up to resolution
Two sequential platelet counts $< 75,000$ platelets/mm ³ ;	Treatment with all study drugs will be discontinued and the subject withdrawn from this study. Follow up to resolution
2 sequential neutrophil counts < 1000 cells/mm ³	Treatment with all study drugs will be discontinued and the subject withdrawn from this study. Follow up to resolution
Confirmed lymphocyte counts < 500 lymphocytes/mm ³ by repeat testing	Treatment with all study drugs will be discontinued and the subject withdrawn from this study. Follow up to resolution
Confirmed increases in serum creatinine $> 50\%$ over the average of screening and baseline values and the absolute value of serum creatinine is above upper limit of normal range.	Treatment with all study drugs will be discontinued and the subject withdrawn from this study. Retesting should occur until the serum creatinine is within 10% of the pretreatment value.
Serious infections defined as any infection (viral, bacterial, or fungal) requiring parenteral antimicrobial therapy or hospitalization for treatment, or meeting other criteria that require the infection to be classified as a serious adverse event.	Treatment with all study drugs will be discontinued and the subject withdrawn from this study
Opportunistic infection judged significant by investigator	Treatment with all study drugs will be discontinued and the subject withdrawn from this study

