8.2.2. Abnormal Test Findings

Abnormal objective test findings should be recorded as AEs when any of the following conditions are met:

- Test result is associated with accompanying symptoms; and/or

- Test result requires additional diagnostic testing or medical/surgical intervention; and/or
- Test result leads to a change in study dosing (outside of any protocol-specified dose adjustments) or discontinuation from the study, significant additional concomitant drug treatment, or other therapy; and/or
- Test result is considered to be an AE by the investigator or sponsor.

Merely repeating an abnormal test, in the absence of any of the above conditions, does not constitute an AE. Any abnormal test result that is determined to be an error does not require recording as an AE.

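### Section 7.6.2 makes the absence of a BUN rise a condition for potential acute kidney injury, so a patient with both creatinine and BUN raised is discontinued but, read literally, is not a case

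*Protocol*

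**What the plan says.** Protocol Section 7.6.2 opens with a definition. It covers "Abnormal values in serum creatinine (SCr) concurrent with absence of increase in BUN (blood urea nitrogen) that meet the criteria below" and, when no other cause of renal damage is present, says these "are considered potential cases of acute kidney injury and should be considered important medical events".

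The criteria that follow use creatinine alone. A rise of at least 0.3 mg/dL over the patient's own baseline triggers a repeat creatinine. If the repeat reaches at least 0.4 mg/dL, "the subject should be discontinued from the study and adequate, immediate, supportive measures taken to correct apparent acute kidney injury". BUN first appears as a requested test in the evaluation after that confirming result. A later sentence classes as potential drug-induced kidney injury "All cases confirmed on repeat testing as meeting the laboratory criteria for acute-kidney-injury", where no other cause is identified.

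Two other sections act on renal findings:

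- Section 6.3 lists as a reason for discontinuation "Any laboratory (defined by changes in serum creatinine or eGFR) or clinical manifestation of acute renal injury", with a pointer to 7.6.2.
- Section 7.7 has two creatinine rows. The first begins "Any serum creatinine increase >50% over the average of screening" and baseline values, with an absolute rise above 0.3 mg/dL as the alternative. It leads to a retest and then the same 0.4 mg/dL discontinuation rule. The second withdraws the patient for a confirmed rise of more than 50% "over the average of screening and baseline values and the absolute value of serum creatinine is above upper limit of normal range".

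**The concern.** The definition and the actions do not select the same patients. A concurrent BUN rise takes a patient out of the definition but leaves every action in place. Section 7.6.2 thus discontinues a patient for what it calls apparent kidney injury while its own opening sentence leaves that patient out of the potential cases.

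The clause is not needed to screen out other explanations, because the same sentence already has a separate proviso for other causes. No visible text explains why a second raised renal marker should remove the label.

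The label matters because, in the visible text, this is the only sentence that gives a creatinine rise a fixed seriousness class; 6.3 and 7.7 set actions only. Important-medical-event status leads towards serious adverse event reporting within 24 hours (8.1, 8.2.3). Without it, seriousness depends on each investigator's judgment or a later sponsor upgrade. If the event is judged non-serious, the table in 8.1 requires no 24-hour report. Sites with identical creatinine results could therefore classify them differently. Renal monitoring is also a declared priority: Amendment 1 added visits at Weeks 6, 10 and 14 to look for urinary crystals and evidence of kidney injury.

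**Working it through.** This is a question of wording, so there is no plan figure to reproduce. The check applies each rule to the same patients and compares the results.

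**Thresholds.** Using 88.4 µmol/L per mg/dL for creatinine, 0.3 × 88.4 = 26.5 and 0.4 × 88.4 = 35.4 µmol/L. Both match 7.6.2, so the creatinine limits are consistent in the two units.

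**Rules as applied.** The 0.4 mg/dL limit is read as a rise over baseline.

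- Retest (7.6.2): first rise ≥ 0.3 mg/dL.
- Discontinue (7.6.2): first rise ≥ 0.3 and repeat rise ≥ 0.4 mg/dL.
- Discontinue (7.7, first row): first rise > 0.3 mg/dL or > 50%, and repeat rise ≥ 0.4 mg/dL.
- Label (7.6.2 opening sentence): first rise ≥ 0.3 mg/dL, no BUN increase and no other cause.

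With an assumed baseline creatinine of 0.8 mg/dL and no other cause found:

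| First rise, repeat rise (mg/dL) | BUN rises | Retest 7.6.2 | Discontinue 7.6.2 | Discontinue 7.7 | Label, as written | Label, BUN clause removed |
|---|---|---|---|---|---|---|
| 0.2, 0.2 | no | no | no | no | no | no |
| 0.3, 0.3 | no | yes | no | no | yes | yes |
| 0.35, 0.45 | no | yes | yes | yes | yes | yes |
| 0.5, 0.5 | no | yes | yes | yes | yes | yes |
| 0.2, 0.2 | yes | no | no | no | no | no |
| 0.3, 0.3 | yes | yes | no | no | **no** | yes |
| 0.35, 0.45 | yes | yes | yes | yes | **no** | yes |
| 0.5, 0.5 | yes | yes | yes | yes | **no** | yes |

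The action columns are the same whether or not BUN rises. Only the label as written changes. Removing the clause brings it back into line in every row.

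**Worked pair (values assumed).** Screening and baseline creatinine are both 0.8 mg/dL, the two on-treatment values are both 1.3, and the upper limit of normal is 1.2.

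- Absolute rise: 1.3 − 0.8 = 0.5 mg/dL. This meets the retest and discontinuation limits.
- Relative rise: 0.5 / 0.8 = 62.5%, above 50%, with 1.3 > 1.2. The second creatinine row of 7.7 also withdraws the patient.
- Patient A, BUN 14 to 14 mg/dL: potential AKI and important medical event.
- Patient B, BUN 14 to 15 mg/dL: same retest and same discontinuation, but neither label.

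**Where the condition can apply.** Table 9 puts BUN and creatinine in the same chemistry panel, and the Schedule of Activities draws it at all eight post-baseline visits (Weeks 1, 4, 6, 8, 10, 12, 14 and 16).

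**The case against.** A stopping rule wider than a case label is not in itself an error, and this protocol does the same for the liver. Section 7.7 withdraws patients for two transaminase values of at least 5 × ULN whatever the bilirubin, while 8.4.2 reserves important-medical-event status for transaminase plus bilirubin. The liver definition also has excluding conditions (haemolysis, raised alkaline phosphatase). That is fair. But in 8.4.2 the second marker of organ dysfunction, bilirubin, brings a case in. In 7.6.2 the second renal marker takes it out, and no reason is visible.

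The label is also less automatic than it looks. Even with BUN flat, ruling out other causes takes judgment. Section 8.2.3 leaves room for judgment, 8.4.1 says there are no protocol-specified serious events, and 7.6.2 lacks the explicit reporting instruction that liver cases get. This stands, and it narrows the gap between Patients A and B.

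Patient B is not lost to safety follow-up. Section 8.2.2 makes the finding an adverse event through its criterion "Test result leads to a change in study dosing (outside of any protocol-specified dose adjustments) or discontinuation from the study". The sponsor may upgrade it, and Section 9.5 summarises events that trigger withdrawal. The two-subject adverse-reaction check in 7.6.2 also uses creatinine alone. All of this stands.

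Section 6.3 defines laboratory renal injury by creatinine or eGFR and points to 7.6.2. That suggests the later 7.6.2 sentence on laboratory criteria may bring Patient B back as potential drug-induced injury. It is a reasonable reading, but 7.6.2 does not say so, and that sentence gives no important-medical-event status.

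A clinician might also disregard a 1 mg/dL change in BUN. The text gives no threshold to support doing so.

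Finally, text after 7.6.2 and within the renal criterion of 6.3 is redacted and could hold a rationale. The finding is therefore confined to what can be read.

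**Conclusion.** The concern holds. Followed exactly, the opening sentence of 7.6.2 leaves out a patient with a qualifying creatinine rise and any concurrent BUN increase, while every visible renal action rule treats that patient the same as one with BUN unchanged. The sentence excludes by definition; it does not expressly say such a patient has no kidney injury.

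The impact is modest. It falls on consistent classification and on the important-medical-event route to 24-hour reporting. Patient-protection actions, adverse event recording, planned safety summaries and efficacy analyses do not change. The number of patients affected cannot be estimated, because the documents give neither an expected frequency of creatinine rises nor the share that would come with a BUN rise. The conclusion assumes a literal reading of the sentence and that no redacted text overrides it. It should be fixed because a stated rule gives the wrong class when applied as written.

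**What to change.** In the opening sentence of 7.6.2, delete the clause requiring no BUN increase, or replace it with *with or without an increase in BUN*. Add that the laboratory criteria named later in the section are its creatinine criteria. Keep BUN in the follow-up evaluation as information on cause. The proviso on other causes can stay.

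The cost is one clause of protocol wording and a letter to sites. No tests are added. The only downside is that a few more events may be flagged as important medical events.

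### Protocol sections 7.6.2, 7.7 and Appendix 6 state the creatinine retest rule with different reference values, comparators and retest times

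*Protocol*

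**What the plan says.** **Section 7.6.2.** The rule is that "An increase of ≥ 0.3 mg/dL" over the subject's "own baseline measurement should trigger another assessment of SCr as soon as practically feasible, preferably within 48-hours from awareness". If the second assessment then reaches 0.4 mg/dL or more, the subject leaves the study.

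**Section 7.7, first creatinine row.** The condition is a rise of more than 50% "over the average of screening (most recent value prior to baseline) and baseline values OR an absolute increase in serum creatinine >0.3 mg/dL" over that same average. The retest is due "ideally within 3-5 days". The action cell then repeats the 0.4 mg/dL discontinuation step in the words of 7.6.2. There the first observation is described as a rise of at least 0.3 mg/dL "in serum creatinine relative to subjects' own baseline measurement) is" at or above the second threshold. So the condition cell uses the average and the action cell uses the subject's own baseline.

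**Appendix 6.** Retesting within one week is required for a creatinine rise of more than 30% and more than 0.2 mg/dL from baseline.

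**Precedence.** The amendment log at the front of the protocol says that the acute kidney injury responses in 7.6.2 supersede those in 7.7, and that the 7.7 creatinine values were updated to match. Section 6.3 points to 7.6.2 for discontinuation after acute renal injury. The readable text of 7.6.2 and 7.7 does not say which governs. Text between the two sections is redacted.

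**The concern.** The retest is the gate to the 0.4 mg/dL discontinuation step. Section 7.6.2 also asks for an adverse drug reaction assessment when two or more subjects have two consecutive results of at least 0.3 mg/dL, and that sentence names no reference value. The amendment log records that visits at Weeks 6, 10 and 14 were added after US regulatory feedback, to watch more closely for kidney injury.

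A site working from the 7.7 table and a site working from 7.6.2 could treat the same laboratory result differently: retest or not, and on a different clock. Section 7.6 is headed for PF-06650833 and 7.7 carries no drug restriction. In a double-blind trial a site cannot tell which subjects would fall outside 7.6, so both rules reach every subject in practice.

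**Working it through.** **Units first.** With an assumed conversion of 88.4 µmol/L per mg/dL, 0.3 × 88.4 = 26.5 and 0.4 × 88.4 = 35.4. These are the printed values, so the units are not the source of the conflict.

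**The rules.** Let S = screening, B = baseline, A = (S + B)/2 and x = on-study creatinine, in mg/dL.

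- 7.6.2 fires if x − B ≥ 0.3.
- 7.7 fires if x − A > 0.3 or x > 1.5A. The 50% limb gives the lower threshold only if 1.5A < A + 0.3, that is, A < 0.6.
- Appendix 6 fires if x > 1.3B and x − B > 0.2.

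Only the numerical conditions are compared. The qualifiers in 7.6.2 on blood urea nitrogen and other causes are left aside. The values of S, B and x are illustrative and do not come from the documents.

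| S | B | x | x − B | x − A | x/A − 1 | x/B − 1 | 7.6.2 | 7.7 | App. 6 |
|---|---|---|---|---|---|---|---|---|---|
| 1.00 | 0.80 | 1.15 | 0.35 | 0.25 | 27.8% | 43.75% | yes | no | yes |
| 0.70 | 0.90 | 1.15 | 0.25 | 0.35 | 43.75% | 27.8% | no | yes | no |
| 0.80 | 0.80 | 1.10 | 0.30 | 0.30 | 37.5% | 37.5% | yes | no | yes |
| 0.80 | 0.80 | 1.08 | 0.28 | 0.28 | 35% | 35% | no | no | yes |
| 0.80 | 0.80 | 1.15 | 0.35 | 0.35 | 43.75% | 43.75% | yes | yes | yes |

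Rows 1 and 2 disagree because of the reference value, once in each direction. Row 3 disagrees because one comparator includes equality and the other does not. In row 4 only Appendix 6 fires. In row 5 all three fire, with three retest times: 48 hours from awareness, 3–5 days (no starting point stated) and one week.

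**How much the reference value matters.** The two absolute thresholds differ by A − B = (S − B)/2. Take creatinine of 0.8 mg/dL and independent measurements with a within-person CV of 5% (an assumption; the documents give none):

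- SD of one value = 0.8 × 0.05 = 0.04
- SD of (S − B)/2 = 0.04 × √2 / 2 = 0.028 mg/dL
- as a share of the trigger, 0.028 / 0.3 = 9%

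Halving the CV to 2.5% gives 0.014 mg/dL (5%). Doubling it to 10% gives 0.057 mg/dL (19%).

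The gap of 0.20 between screening and baseline in rows 1 and 2 is 0.20 / (0.04 × √2) = 3.5 SD at a CV of 5%, and 1.8 SD at 10%. Those rows show that the rules can disagree, not that they often will. The clash in retest times needs no such gap.

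**The case against.** **Precedence is already given.** The amendment log states it, and section 6.3 points the same way. A log describes past changes, and a difference between it and the current text is not in itself an error. The point does not rest on such a difference: 7.6.2 and 7.7 conflict as they now stand. The log does show what was intended, which lowers the severity and makes the repair easier. A precedence statement in the redacted text cannot be excluded.

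**The rules can coexist.** A site could retest when either condition is met, and both times are soft targets. That is fair, but the protocol does not tell sites to read it so, and whether they should is for the sponsor's clinicians.

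**Three stronger readings a reader might infer are not supported.**

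- *That 7.6.2 and 7.7 give different withdrawals at 0.4 mg/dL.* That step has the same wording in both. In row 2 the rise over own baseline is 0.25, so the first observation named in the 7.7 action cell is not met under either section. Section 7.7 has a further discontinuation row (a confirmed rise of more than 50% over the average, with a value above normal). It has no counterpart in 7.6.2, so it is an addition and not a second version of the 0.4 step.
- *That kidney cases would be counted differently by dose.* Nothing in the documents ties a blinded site's choice of section to the assigned dose.
- *That a SAP analysis is compromised.* The readable SAP defines no creatinine case count. It refers laboratory summaries to the sponsor's reporting standards.

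**Conclusion.** The retest rule for a creatinine rise is internally inconsistent in the current protocol, and this can be checked word for word. Sections 7.6.2 and 7.7 differ in reference value, comparator and retest time; the 7.7 row uses two reference values within itself; Appendix 6 adds a third rule.

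The conflict shown between 7.6.2 and 7.7 is limited to who is retested and how soon. The difference in timing is certain for every subject who meets both rules. The difference due to the reference value is usually small, about 0.03 mg/dL. That figure rests on an assumed CV of 5% at 0.8 mg/dL and moves in proportion to the CV.

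This is a wording repair that should be made to a safety instruction. It does not bear on the efficacy analysis.

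**What to change.** Reconcile section 7.6.2, the creatinine rows of 7.7 and the creatinine item in Appendix 6, so that each creatinine trigger has one reference value, one comparator and one retest interval with a stated starting point. State in the body text, not only in the amendment log, which section governs. Name the reference value in the 7.6.2 sentence on two consecutive results.

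A bare cross-reference from 7.7 to 7.6.2 would not be enough. It would silently drop the 50% condition, which 7.6.2 does not have. The sponsor's clinicians choose the rule and should decide explicitly what happens to that condition. This review takes no view on which reference, threshold or interval is right.

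The cost is a few lines of text in three places and a memo to sites. As a protocol amendment it also needs ethics approval under section 12.1, so it is best combined with the next amendment. No new data collection is needed.

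### The creatinine stopping threshold (Protocol 7.6.2 and 7.7) and the two-subject threshold (7.6.2) are printed as plain values although a rise over baseline is meant

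*Protocol*

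**What the plan says.** Protocol 7.6.2 contains three creatinine thresholds.

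- **Recheck.** "An increase of ≥ 0.3 mg/dL" (26.5 µmol/L) relative to the subject's own baseline prompts another creatinine measurement, preferably within 48 hours.
- **Stop.** The sentence opens "If the second assessment (after the 1st observations of ≥ 0.3 mg/dL" and continues, after the µmol/L figure and the baseline reference, "own baseline measurement) is ≥ 0.4 mg/dL" (35.4 µmol/L). The consequence is discontinuation from the study.
- **Two-subject rule.** If two or more subjects have two consecutive "SCr results of ≥ 0.3 mg/dL", the possibility of an adverse drug reaction is to be assessed. That sentence does not mention baseline.

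The action cell of the creatinine row in Protocol 7.7 repeats the stopping sentence: "own baseline measurement) is ≥0.4 mg/dL". The condition cell of the same row is worded as an increase over the average of the screening and baseline values. Protocol 6.3 lists as a reason for discontinuation "Any laboratory (defined by changes in serum creatinine or eGFR) or clinical manifestation of acute renal injury" and refers to 7.6.2.

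**The concern.** The first threshold is a rise. The other two, as printed, are levels. In the stopping sentence the baseline reference belongs to the bracket describing the first observation. Once the bracket closes, what must reach 0.4 mg/dL is the second assessment itself, and the preceding sentence calls that a measurement of serum creatinine. The two-subject rule speaks of results, not of increases.

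The recheck exists to separate a transient rise from a confirmed one. A fixed level of 0.4 mg/dL cannot do that for any subject whose baseline is already 0.4 mg/dL or more. Kidney injury is a specific concern here: according to the summary of changes, Amendment 1 added the Week 6, 10 and 14 visits to monitor for it. The wording also bears on more than treatment. Under 7.6.2, cases confirmed as meeting the laboratory criteria, with no other cause found, are to be considered potential drug-induced kidney injury. Under Protocol 9.2, a dropout attributed to an adverse event has the missing SDAI score set to baseline.

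**Working it through.** **1. Are the numbers sound?** The two unit pairs give 26.5/0.3 = 88.3 and 35.4/0.4 = 88.5 µmol/L per mg/dL. They agree, so this is not a unit misprint. Only the reference point is missing.

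**2. Which reading is meant?** The surrounding text points one way:

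- The recheck trigger in 7.6.2 is an increase over own baseline.
- 6.3 speaks of changes in creatinine: "Any laboratory (defined by changes in serum creatinine or eGFR) or clinical manifestation of acute renal injury".
- 7.6.2 places the follow-up evaluation after "awareness of the second assessment confirming abnormal SCr result", so the recheck is meant to confirm something.
- The condition cell in 7.7 and the retest list in Appendix 6 are both worded as increases.
- Where 7.7 does mean a level, it says so: "the absolute value of serum creatinine is above upper limit of normal range".

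The intended stop is therefore baseline + 0.4 mg/dL.

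**3. What does the printed rule do?** The documents give no baseline creatinine, so b below is an assumption. The recheck trigger is b + 0.3, the literal stop is 0.4 and the intended stop is b + 0.4. To escape the literal stop, the recheck must lie more than (b − 0.4)/b below baseline.

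| Assumed b (mg/dL) | Recheck trigger | Literal stop | Intended stop | Fall below baseline that must be exceeded |
|---|---|---|---|---|
| 0.5 | 0.8 | 0.4 | 0.9 | 0.1/0.5 = 20% |
| 0.8 | 1.1 | 0.4 | 1.2 | 0.4/0.8 = 50% |
| 1.0 | 1.3 | 0.4 | 1.4 | 0.6/1.0 = 60% |
| 1.1 | 1.4 | 0.4 | 1.5 | 0.7/1.1 = 64% |

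The protocol's µmol/L figures give the same picture at assumed baselines of 45, 70 and 97:

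- (45 − 35.4)/45 = 21%
- (70 − 35.4)/70 = 49%
- (97 − 35.4)/97 = 64%

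The two readings disagree for every recheck from 0.4 up to just under b + 0.4 mg/dL, a band of width b. At b = 0.8:

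- Recheck 0.8 (full recovery): stop literally, continue as intended.
- Recheck 1.1 (rise still 0.3): stop literally, continue as intended.
- Recheck 1.2 (rise 0.4): stop on both readings.

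**4. Direction of the error.** For every b > 0, b + 0.4 exceeds 0.4. Any recheck that meets the intended stop therefore also meets the literal one. The error over-stops and never misses an intended stop.

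**5. Two-subject rule.** The Schedule of Activities has blood chemistry at Weeks 1 and 4, so two consecutive on-treatment results exist by Week 4. Read literally, any two subjects with stable creatinine of 0.3 mg/dL or more satisfy the rule. As intended, at b = 0.8, both results would have to be 1.1 mg/dL or more.

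**The case against.** The best defence is that no clinician would read the sentence literally. Protocol 6.3 refers to 7.6.2 by number and calls the laboratory criterion a change. Inside the bracket, 7.6.2 has already dropped the word for an increase while plainly meaning one, so the later phrases could be the same shorthand. The section opens by restricting potential cases to abnormal creatinine values without a rise in BUN and without other causes, which does not describe a subject back at baseline. Some text after the two-subject sentence, and some after the cross-reference in 6.3, is blacked out and might clarify matters. The calculations quantify a reading that nobody intends.

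Most of this stands as evidence of intent, and it limits the importance of the point. Hidden clarification cannot be excluded. But the sentences at issue are visible and complete, and nothing visible corrects them. A reader who supplies the missing reference also meets two candidates in the 7.7 row: the average of screening and baseline, and own baseline. With an assumed screening value of 1.0 and baseline of 0.8 mg/dL, the stop would be 0.9 + 0.4 = 1.3 on the average and 0.8 + 0.4 = 1.2 on own baseline. The summary of changes says that 7.6.2 takes precedence over 7.7 for acute kidney injury triggers. That makes the 7.6.2 wording the natural one to correct, although the defect does not depend on that statement because both sections carry it.

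**Conclusion.** The point holds: the stopping threshold in 7.6.2 and 7.7, and the two-subject threshold in 7.6.2, are wrong as written. Literal and intended stops differ by the whole baseline value, for example 0.4 against 1.2 mg/dL at an assumed baseline of 0.8. The baselines are assumptions; the direction of the error is not, since it holds for any positive baseline.

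The practical impact is probably small. The intent is clear, no intended stop is lost, 6.3 calls for consultation with the sponsor's clinical team, and the two-subject rule starts only an assessment. The documents do not say how many subjects would reach a first trigger, so the number of needless stops cannot be estimated. A misworded threshold in a discontinuation rule should still be corrected.

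**What to change.** Keep every threshold, and leave the baseline definition in the 7.7 condition cell as it is. Change three sentences:

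- In 7.6.2 and in the 7.7 action cell: *If the second assessment shows an increase of ≥0.4 mg/dL (≥35.4 µmol/L) relative to the subject's own baseline*, followed by the existing consequence.
- In the two-subject rule of 7.6.2: *2 consecutive SCr increases of ≥0.3 mg/dL (≥26.5 µmol/L) relative to the subject's own baseline*.

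The cost is a few words in an amendment or a letter to sites. No visit or test changes.
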